5.4.2 HANDLING OF PARTICIPANT WITHDRAWALS OR TERMINATION

Participants may withdraw or terminate involvement at any time for any reason, and that request will be honored.

No discontinuation visit is necessary. However, participants who terminate or withdraw for toxicity reasons will be followed for that toxicity until the toxicity is resolved.

5.5 PREMATURE TERMINATION OR SUSPENSION OF STUDY

This study may be temporarily suspended or prematurely terminated at the discretion of the study team. Study participants will be informed of study suspension or termination and whether the circumstances that led to this decision confers possible added risk to study participants.

Regulatory authorities including the IRB, the Food and Drug Administration (FDA), and ClinicalTrials.gov will be notified as warranted.

[figure not shown]
6 STUDY AGENT

6.1 STUDY AGENT AND CONTROL DESCRIPTION

6.1.1 FORMULATION, APPEARANCE, PACKAGING, AND LABELING

Telmisartan is a non-peptide angiotensin II receptor (type AT1) antagonist.

It is chemically described as 4'-[(1,4'-dimethyl-2'-propyl [2,6'-bi-1H-benzimidazol]-1'-yl)methyl]-[1,1'-biphenyl]-2-carboxylic acid. Its empirical formula is C₃₃H₃₀N₄O₂, its molecular weight is 514.63, and its structural formula is:

Telmisartan is a white to slightly yellowish solid. It is practically insoluble in water and in the pH range of 3 to 9, sparingly soluble in strong acid (except insoluble in hydrochloric acid), and soluble in strong base

Telmisartan is available as a patented drug originally FDA approved in 1998 and marketed under the trade name Micardis. Multiple different generics are also available with tablets varying in size, color, and shape. The appearance, packaging and labeling also differs by the generics on the market. This study will select and utilize one specific formulation for all its needs.

6.1.2 PRODUCT STORAGE AND STABILITY

Store at 25°C (77°F); excursions permitted to 15°-30°C (59°-86°F)

6.1.3 PREPARATION

Study medication to be dispensed to participants will be prepared by the research pharmacist. Telmisartan and matching placebo will be prepared using over-encapsulation.

6.1.4 DOSING AND ADMINISTRATION

Telmisartan will be dosed in this study as one tablet of 40 mg to be taken by mouth daily. All study medication will be dispensed to the study participant by the research pharmacist provided to the participant by the research nurse.

6.1.5 ROUTE OF ADMINISTRATION

Study drug will be taken orally with or without food.

6.1.6 STARTING DOSE AND DOSE ESCALATION SCHEDULE

Participants will be randomized to one 40 mg tablet of Telmisartan daily or one placebo tablet daily. There is no dose reduction or escalation for this study.

6.1.7 DOSE ADJUSTMENTS/MODIFICATIONS/DELAYS

The toxicity grading system that will be used is the Division of AIDS Table for Grading the Severity of Adult and Pediatric Adverse Events, Version 2.0, November 2014, located at:

6.1.8 DURATION OF THERAPY

The study medication will be given for a duration of 21 days.

6.1.9 TRACKING OF DOSE

Subjects will be asked to bring back any medication not taken.

6.1.10 DEVICE SPECIFIC CONSIDERATIONS

Not applicable.

6.2 STUDY AGENT ACCOUNTABILITY PROCEDURES

Drug Accountability

The pharmacist will be responsible for ensuring adequate accountability of all used and unused study drug. This includes ordering and acknowledgment of receipt of study product (quantity and condition), subject dispensing records and returned or destroyed study product. Accountability records will document quantities including lot number, date dispensed, subject identifier number, subject initials, and the initials of the person dispensing the medication. Study drug will not be supplied to any person who has not consented to participate in the study. Persons authorized to distribute and control the study medication include the PI or Co-I listed on the FDA 1572 and designated staff.

Unused Study Drug

Upon study completion, unused study drug will be destroyed at the research unit (verified by witness). Original drug accountability records must be maintained in the site's records.

Placebo

Tentative plans for placebo call for the use of gelatin capsules filled with an inactive ingredient. To provide a similar appearance, telmisartan tablets will be over-encapsulated with the gelatin capsules.

6.3 STUDY PROCEDURES/EVALUATIONS

6.3.1 STUDY SPECIFIC PROCEDURES

Study specific procedures include obtaining oropharyngeal swabs and research blood specimens.

6.3.2 STANDARD OF CARE STUDY PROCEDURES

Other than monitoring safety labs to assess lack of adverse events on study medication, this protocol is not meant to provide clinical care of patients with COVID-19 disease.

6.4 LABORATORY PROCEDURES/EVALUATIONS

6.4.1 CLINICAL LABORATORY EVALUATIONS

Hematology: Complete blood count (CBC)

Chemistries: Chemistry to include sodium (Na), potassium (K), chloride (Cl), bicarbonate (HCO₃), creatinine, blood urea nitrogen (BUN), aspartate aminotransferase (AST), aminotransferase (AST), alkaline phosphatase (ALK-P), total bilirubin, albumin, and glucose. In addition, LDH and hs-CRP will be assessed serially.

6.4.2 OTHER ASSAYS OR PROCEDURES

Research bloods will be drawn, processed to separate into viably preserved PBMC and plasma, and banked for batch analyses of the following:

RAS assessments: Assessments of various components of the RAS system will be performed in [name] lab. This is anticipated to include RAS peptides to be drawn in protease inhibitor containing tubes to include AngI, AngII, Ang(1-9) and Ang(1-7); ACE1 and ACE2 in plasma; and ACE1, ACE2, AT1R, AT2R and MasR in PBMC. In addition, one cc of plasma will be forwarded to [name] lab for ACE1 and ACE2 enzymatic evaluation. A vial of 5 million cells will be forwarded for RT-PCR for AT1R, AT2R, MasR, ACE1 and ACE2 as well as neprilysin (NEP) and aminopeptidase A (APA).

Plasma Biomarkers: Blood plasma will be assessed for plasma biomarkers of organ function/coagulation, inflammation, leukocyte chemotaxis, tissue remodeling/fibrosis and immune exhaustion by Luminex multiplexing assays. While subject to change the following analytes are planned:

Organ Function/Coagulation	Inflammation		Leukocyte Chemotaxis	Tissue Remodeling/Fibrosis	Immune Exhaustion
CKMB	CRP	TNF- α	Fractalkine/CX3CL1	MMP-1	TIM-3
LDH-B	Ferritin	TNF-RI	MCP-1/CCL2	MMP-7	Galectin-9
NTproBNP	IL-1 β	TNF-RII	MCP-3/CCL7	PDGF-BB	PD-1
Troponin I	IL-1ra	M-CSF	MIP-1 α /CCL3	CHI3L1/YKL-40	PD-L1
Myoglobin	IL-2	G-CSF/CSF-3	MIP-1 β /CCL4	LAP	CD152/CTLA-4
KL-6	IL-2R	IDO	MIP-2 α /CXCL2	TIMP-1	PVR
SP-A	IL-4	TWEAK	IP-10/CXCL10	PAI-1/Serpin	VISTA/B7-H5
SP-D	IL-6	TREM-1	IL-8/CXCL8		GITR
D-dimer	gp130/IL-6RB	PTX-3	ICAM-1		BTLA
tPA	IL-7	TSLP	VCAM-1		
	IL-9	Siglec-9	E-selectin/CD62E		
	IL-10	NGAL	MIG/CXCL9		
	IL-17A/CTLA-8	Galectin-3	CCL18/PARC		
	IL-33R/ST2	MPO			
	IFN- γ	PRDX4			

Oro-pharyngeal Swab: Oro-pharyngeal swabs will be obtained at each study timepoint. These will be collected using a foam swab and placed in a multi microbe media (M4, M4RT, M5, M6), VCM (UTM) medium (green-top) tube, Amies liquid elution swab (ESwab), or equivalent Viral Transport Media (VTM). Once placed in the appropriate viral media, the specimens will be frozen at -70C and sent out for batch analysis at a later date. While it is currently anticipated that the study will utilize oro-pharyngeal swabs for determination of viral persistence, it is possible that naso-pharyngeal swabs or saliva testing or other means of viral detection may be substituted depending on sensitivity/specificity, availability, and cost.

6.4.3 SPECIMEN PREPARATION, HANDLING, AND STORAGE

6.4.3.1 Blood Draw

Collection of blood will occur at the specified time points for clinical laboratory assessments and for research blood for assays to be conducted on cryopreserved blood. The quantity of blood to be drawn at each setting is defined in the Schedule of Events.

Whole blood will be obtained by venous puncture and processed by the Processing Laboratory ideally within 1 hour of collection. If processing will be delayed (2-3 hours), the collection tube should be placed on a slow rocking table until processed.

6.4.3.2 Blood for RAS assessments

Blood will be drawn in specific tubes pre-filled with protease solution to enable to determine of various RAS components. These pre-filled tubes will be obtained from [name] laboratory and will be forwarded to his lab in Los Angeles for RAS analyses.

6.4.3.3 Plasma (EDTA tube) for banking

Plasma is separated from whole blood collected in EDTA vacutainers.

1. Spin vacutainer at 900xg for 10 minutes at room temperature (RT) to separate plasma from blood cells.
2. Remove plasma and save tube to process white blood cell separation.
3. Transfer plasma to a labelled 15mL conical Falcon tube and centrifuge at 820xg for 10 minutes at 4°C.
4. Aliquot plasma into 1mL labelled cryovials (3 to 4 aliquots).
5. Cryovials are stored at -20°C for 24 hours before being transferred to long-term cryobox storage at -80°C or placed in liquid nitrogen Dewar to snap freeze.

6.4.3.4 Peripheral Blood Mononuclear Cells (PBMC)(EDTA tube)

1. Resuspend EDTA blood pellet after plasma separation with 2x DMSO freezing medium in 1:1 ratio and freeze in 1 mL aliquots at -80°C after counting total WBCs for use in chloramine analysis assay.
2. Follow standard Ficoll Hypaque procedure to separate PBMC from 10 mL of heparinized blood.
3. Perform a cell count of the isolated PBMC.
4. Add appropriate DMSO/FBS solution for a final concentration of 5×10^6 cells/mL.
5. Transfer 1mL aliquots (5×10^6 cells) to 1.25 mL cryovials. Store in [name] at -80°C for at least 24 hours before transferring samples to long-term -140°C storage.

6.4.4 SPECIMEN SHIPMENT

Blood tubes for RAS assessment will be shipped to [name] lab at a minimum of q monthly intervals. Plasma and viably preserved PBMC will also be forwarded to [name] lab for the planned extended analysis of the RAS components.

6.4.5 SCREENING

6.4.5.1 Initial Medical History by Phone Interview

Verbal informed consent and medical history will be obtained by phone or video-conference (selected at caller preference) interview with the potential participant. The interview will record:

- Current Illness: Obtain date of onset of current illness, date of SARS-CoV2 testing and date the positive test was reported back to the participant. Review participant's signs and symptoms associated with the illness with a focus on presence, course, and severity of fever, dyspnea and fatigue. Record grade of fever, dyspnea and fatigue on symptoms scale.
- History of co-morbidities including history of cardiovascular disease including history of hypertension, history of pulmonary diseases; history of pre-diabetes or diabetes, history liver, kidney disease or auto-immune/ immune deficiency diseases and history of alcohol, tobacco, or illicit substance abuse
- Current prescription and over-the-counter medications and medication allergies
- Self-reported weight and height

The potential participant will be asked to bring his or her COVID-19 test result to the person-to-person screening/entry visit. If documentation of the COVID-19 test result is unavailable, the potential participant will be given the option of obtaining it or providing the researchers permission to obtain the test result (this will be done at the Entry visit).

6.4.6 FOLLOW-UP SCREEN AND ENROLLMENT/BASELINE [ENTRY VISIT (VISIT 1, DAY 1)]

Potential participants who have verbally consented to the study will be given an appointment for a follow-up person-to-person screening/entry visit as soon as possible – preferably the same day. The screen/entry visit should occur within 24 hrs of the telephone screening visit.

This screen/entry in-person visit will preferably be conducted outside with the participant in his/her car or sitting comfortably in a portable tent set up in the clinic parking area of the UH Clinics at Kakaako. Study visits in other venues will be considered on a case-by-case basis. It is envisioned that such visits in other venues may occur if the participant is not able to come to the UH Clinics at Kakaako parking area in a safe manner. Study visits in other venues will occur only if the participant is willing and the setting can a) ensure participant safety; b) will not increase risk of infection or pose any other safety issues for our clinical research staff; c) will ensure adequate privacy for the participant; d) the location will allow satisfactory performance of all study mandated procedures; and e) will not break any state or county law or ordinance. A 'safe' study visit location away from the UH Clinics at Kakaako premises may include, for example, an outside patio open to outside air flow attached to the participant's home located within the immediate Honolulu area (i.e. not a distance which may make blood transport back within a reasonable time frame difficult) that could be assessed without entering the home and would ensure adequate privacy and acceptability for the participant. We will mandate that the PI ([name]), clinical Sub-Investigator ([name]), unit coordinator ([name]), research nurse and all staff physically planning to conduct this study visit in a different venue must ALL be in agreeable that the venue is safe BEFORE a different venue is permitted. If all members of the research team are fully vaccinated (are at least 14 days beyond completion of his/her COVID-19 vaccine series), it may be decided that completing most of the interview by phone but entering the home in full PPE briefly to complete certain research needs (such as a blood draw) may be acceptable.

- Informed consent document will be reviewed. The participant will be provided with the informed consent document, asked to sign and a photo taken of the informed consent signature page.

- The current signs and symptoms will be reviewed and the presence of symptoms sufficient to meet entry requirements will be confirmed. Entry Symptom Scale and Clinical Status to be recorded.
- A photo of the person's COVID-19 test result will be taken. If unavailable and the person opts to have the researchers request it, the person will provide signed permission Consent to Release Information and a photo will be taken of the document. This will permit researchers to obtain the test result document. Also, the person will be asked to sign the Consent to Release in case of hospitalization.

With confirmation of study eligibility:

- Vitals signs will be taken to include temperature, pulse, blood pressure, respiratory rate, and O₂ sat.
- Oro-pharyngeal swab will be obtained
- Blood draw for clinical safety labs and for research assays in quantity as specified in the Schedule of Events.
- The participant will be given a Symptoms log and instructed to daily take and record his/her own blood pressure and temperature. Temperature should also be taken whenever there is tactile fever. The participant will be provided with a digital thermometer and BP monitor as needed and instructed in their use. The participant will be asked to call *immediately* if systolic blood pressure falls below 90 mmHg and to NOT take further study medications unless advised by the study team that it is safe to do so.
- The pharmacist will randomize study participant to telmisartan or placebo; then the study medication will be dispensed to the participant. Participant will be instructed to take first dose as soon as he or she is home.
- Provide the following instructions to participants:
 - Take BP daily at generally the same time of the day and record on Symptoms log. Call research team if SBP is <90 and do not take further study medication unless instructed to do so by the research team.
 - Take temperature whenever a fever is suspected but at least once daily and record
 - Record appropriate fever, dyspnea and fatigue symptoms daily
 - Record the time study medication is taken daily
 - Participants will be advised to take particular effort to remain hydrated, and to be judicious with the use of aspirin or other NSAIDS for fever/symptomatic treatment because it may increase risk for renal problems if excessive amounts are taken with study medication.

6.4.7 FOLLOW-UP STUDY VISITS

The participant will be asked to daily:

- take BP generally at the same time of day and record

- measure temperature prn tactile fever but at least daily and record
- record fever, dyspnea and fatigue

The research nurse will phone or video-conference the participant daily or at least 3x/week during the first week to monitor how the participant is doing especially if there are concerns regarding the participant's status and to reinforce the need to take daily study medications and to record BP, temperature and symptom status.

The participant will also be instructed to call the research nurse (or Physician-on-call on weekends or after-hours via the Physician Exchange Service) if side effects, problems or concerns arise.

Day 4 (+/- 1 day) and Day 10 (+/- 1 day) Study Visit At this visit, nurse will:

- Take photo of participant's log for temperature, BP and symptoms; assess current signs and symptoms and clinical status
- Update medication list
- Record adherence with study medication
- Record AEs as reported by participant or observed by investigator
- Record vital signs (temperature, pulse, blood pressure, respiratory rate and O₂ sat) and conduct targeted PE if warranted
- Collect OP swab
- Draw blood for clinical safety labs and for research assays in quantity as specified in the Schedule of Events.

6.4.8 FINAL STUDY VISIT

Day 21 Study Visit (+/- 2 days) At this visit:

- Take photo of participant's log for temperature, BP and symptoms; assess current signs and symptoms and clinical status
- Update medication list
- Record adherence with study medication
- Collect unused medication
- Record AEs as reported by participant or observed by investigator
- Record vital signs (temperature, pulse, blood pressure, respiratory rate and O₂ sat) and conduct targeted PE if warranted
- Collect OP swab
- Draw blood for clinical safety labs and for research assays in quantity as specified in the Schedule of Events.

6.4.9 FOLLOW UP PHONE CALLS

Post Day 21

- Research nurse may contact the participant after the last study visit if further follow-up information on participant status is needed

6.4.10 DISCONTINUATION OF STUDY TREATMENT

The study treatment will be prematurely discontinued for the following reasons:

- Participant becomes pregnant or starts breast-feeding
- Participant is admitted to the hospital
- Participant requires a prohibited medication

The participant will be asked to continue to be followed and attend the study visits after discontinuation of study treatment. No study procedures will be performed on the participant during hospitalization.

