2 INTRODUCTION: BACKGROUND INFORMATION AND SCIENTIFIC RATIONALE

2.1 BACKGROUND INFORMATION

COVID-19 Pandemic As of the writing of this protocol, there 2,394,278 cases of Covid-19 in 185 countries and regions throughout the world and approximately 83,764 new cases occur daily. In the largest cohort of >44,000 persons with COVID-19 from China, while disease severity was mild to moderate in 81%, pulmonary and multi-organ system dysfunction complications account for the majority of the morbidity and mortality of this disease. Severe disease (dyspnea, hypoxia, or >50% lung involvement on imaging) occurred in 14%, and critical disease (respiratory failure, shock, or multiorgan system dysfunction) occurred in 5%. Among U.S. COVID-19 cases with known disposition, the proportion of persons who were hospitalized was 19%¹. Among patients who developed severe disease, the median time to dyspnea ranged from 5 to 8 days, the median time to acute respiratory distress syndrome (ARDS) ranged from 8 to 12 days, and the median time to ICU admission ranged from 10 to 12 days²⁻⁵. Age is a strong risk factor for severe illness, complication and death¹, and the case fatality is higher for patients with co-morbidities: 10.5% for those with cardiovascular disease, 7.3% for diabetes, and approximately 6% each for chronic respiratory disease, hypertension and cancer⁶.

Figure 1. ‘Deleterious’ and ‘Protective’ Aspects of the Renin-Angiotensin System (RAS)

Compared to other states, Hawaii has had relatively few cases (574 confirmed COVID-19 cases as of April 19, 2020). Early institution of public health measures including the mandatory 14-day quarantine for all individuals flying into Hawaii have been credited for these low number. However, without an effective vaccine, as normalization of the economy and re-opening of our state to visitors are attempted, more cases of COVID-19 may be inevitable.

Renin-Angiotensin System (RAS) RAS is a hormonal system best known for its ability to regulate blood pressure, fluid and electrolyte balance and systemic vascular resistance. As shown in very simplistic form in Figure 1, angiotensinogen, released by the liver, is converted by the action of renin into angiotensin I [AngI; also known as Ang-(1–10)]. AngI is subsequently converted to angiotensin II [AngII; Ang-(1–8)] by the angiotensin-converting enzyme (ACE1) found on the surface of vascular

endothelial cells, predominantly in the lung.

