4.1.1 PRIMARY ENDPOINT

The primary endpoint is the maximum clinical severity of disease for each participant as assessed on a 7-point **Clinical Status** ordinal scale adapted from the WHO MASTER PROTOCOL for the Treatment of COVID-19 in Hospitalized Patients. The WHO 7-point scale was modified by adding sub-categories for the categories of 'Not hospitalized, limitation on activities' (based on scoring on a **Symptom Scale** to be filled out by participants daily, as explained below), as well as for the 'Hospitalized, requiring supplemental oxygen' and 'Hospitalized, on non-invasive ventilation or high flow oxygen devices' categories. For non-hospitalized participants, the maximum clinical severity recorded for any day \geq day 3 of study will be used. For participants who become hospitalized, the maximum clinical severity prior to discharge will be used.

Clinical Status Classification	Score
Not hospitalized, no limitations on activities	1.0
Not hospitalized, limitation on activities as assessed by the Symptom Scale below	
(a) \leq 3 points	2.0
(b) 4-6 points	2.25
(c) 7-9 points	2.5
(d) 10-12 points	2.75
Hospitalized, not requiring supplemental oxygen;	3.0
Hospitalized, requiring supplemental oxygen:	
(a) Requiring supplemental oxygen at < 6 L/min	4.0
(b) Requiring supplemental oxygen at ≥ 6 L/min	4.5
Hospitalized, on non-invasive ventilation or high flow oxygen devices	
(a) Non rebreather mask	5.0
(b) Noninvasive ventilation (NIV), high flow O ₂ devices	5.5
Hospitalized, on invasive mechanical ventilation or ECMO	6.0
Death	7.0

'**Symptom Scale**' to be used for sub-classification of the 'Not hospitalized, limitation on activities' category on the modified WHO 7-point ordinal scale is as shown below. The participant will be asked to daily grade each symptom by severity to obtain a total score. For example, the assessment of grade 2 fever (2 points), grade 1 breathing (1 point) and grade 3 fatigue (3 points) will result in a total score on the symptom scale of 6 for that day. Referring back to the **Clinical Status** classification above, the clinical status on the 7 point ordinal scale would be 'not hospitalized, limitation on activities (b) 4-6 points' for a clinical status score for the participant on that day of 2.25.

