6.4.11 SCHEDULE OF EVENTS TABLE

Schedule of Events	Phone Screen	Entry (Day 1)	Day 4	Day 10	Day 21
Review COVID-19 symptoms and date of COVID-19 testing; Obtain Demographics, verbal Ht and Wt and Co-Morbid Medical History; Obtain Verbal Informed Consent	x				
Update current illness and confirm eligibility for study; verify signing of Informed Consent		x			
Complete Symptom Scale and Clinical Status		x	x	x	x
Vital Signs (Temp, Pulse, BP, Resp Rate, O ₂ sat)		x	x	x	x
Pregnancy test (except in post-menopausal state)		x	x*	x*	x*
Oro-pharyngeal Swab		x	x	x	x
Safety Labs (CBC with diff, chem, hsCRP, LDH) [10 ml]		x	x	x	x
RESEARCH Bloods including for RAS assessment (volume to be drawn) [25 ml]		x	x	x	x
TOTAL BLOOD VOLUME (ml)		35	35	35	35

*If possibility of pregnancy is solicited from participant

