9.3.2 ANALYSIS OF THE PRIMARY EFFICACY ENDPOINT(S)

The efficacy primary endpoint of the study is the maximum clinical severity of disease as assessed by the clinical status ordinal scale. The primary efficacy analysis will be performed using a proportional odds model. This model allows comparing odds ratios on ordinal categories between the experimental treatment and the placebo via a set of regression parameters. The statistical significance of regression parameters will be tested using a one-sided test for the superior efficacy by telmisartan. Alternatively, several ordinal categories can be combined to obtain a composite binary class outcome, in case of insufficient class representations observed. In this situation, group comparison with respect to a binary outcome can be performed using the logistic regression model.

In addition to the primary analysis, longitudinal outcomes obtained at baseline (day 1), days 4, 10, and 21 will be used in a generalized mixed-effect regression model (i.e., cumulative link mixed model) that contains treatment and days, and treatment: days interaction as fixed effects. In the model, treatment: days interaction represents the difference in longitudinal trajectories between the two treatment groups. The statistical significance of interactions will be determined. The regression models used for analysis can be further adjusted for any unbalanced covariates observed at baseline.

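### The plan gives no source for an inpatient's Clinical Status at days 4, 10 and 21, so the supplementary longitudinal model could lose its inpatient scores because of the outcome itself

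*Combined protocol and SAP*

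**What the plan says.** Section 6.4.10 stops study drug on hospital admission and adds, without exception, that "No study procedures will be performed on the participant during hospitalization". The same section keeps these people in follow-up: "The participant will be asked to continue to be followed and attend the study visits after discontinuation of study treatment".

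The Schedule of Events (6.4.11) lists "Complete Symptom Scale and Clinical Status" at entry and at days 4, 10 and 21, alongside the swab and the blood draws. Sections 6.4.7 and 6.4.8 make clinical status one of the tasks at those visits.

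Section 9.3.2 adds to the primary analysis a cumulative link mixed model of the outcomes at days 1, 4, 10 and 21, in which the "treatment: days interaction represents the difference in longitudinal trajectories between the two treatment groups".

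For the primary endpoint, 4.1.1 does provide for inpatients: "For participants who become hospitalized, the maximum clinical severity prior to discharge will be used". The route to the data is in 6.4.6: "Also, the person will be asked to sign the Consent to Release in case of hospitalization".

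On missing data, 9.3.1 offers only exclusion of participants lacking final outcome data and a multiple-imputation sensitivity analysis whose assumptions are not given.

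**The concern.** On the scale in 4.1.1, scores 3.0 to 6.0 exist only for people in hospital. If visit-day Clinical Status is collected only at study visits, and nothing is done at a visit that falls during a hospital stay, none of those scores can be observed in the visit data. Whether a score is missing then depends on the value it would have had. A cumulative link model fitted to such data has no observations from which to place the thresholds between 3.0 and 6.0. If one arm has more admissions, that arm loses more of its worst records, and the treatment-by-day contrast could shrink.

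The same stays remove swabs and blood samples. The RAS, biomarker and viral comparisons at days 4, 10 and 21 would then under-represent participants while they were most ill.

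**Working it through.** **Inputs from the documents (9.4).** Placebo vector {0.40, 0.40, 0.05, 0.04, 0.04, 0.04, 0.03}; telmisartan vector {0.76, 0.18, 0.02, 0.01, 0.01, 0.01}; odds ratio 5.0; 20 per arm. The telmisartan vector has six entries for seven categories and sums to 0.99, so its upper share is given as a range.

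**Plan's own figure first.** Applying an odds ratio of exactly 5 to the placebo vector gives P(category 1) = 5×0.40/(0.60 + 5×0.40) = 0.769 and P(category 2 or lower) = 5×0.80/(0.20 + 5×0.80) = 0.952. A simulated proportional-odds score test (tie-corrected Wilcoxon, 40,000 trials, one-sided 5%) has 79.9% power, against about 80% stated. The planning inputs are therefore usable. With the printed telmisartan vector and the missing 0.01 placed in category 7, power is 76.8%.

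**Participants who reach categories 3 to 7.**
- Placebo: 0.05 + 0.04 + 0.04 + 0.04 + 0.03 = 0.20, and 0.20 × 20 = 4.0.
- Telmisartan: 0.05 as printed, 0.06 with the missing 0.01 added, 0.048 at an exact odds ratio of 5. Times 20, this is 0.95 to 1.2, or about 1.

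**Day 10 scores lost.** Timing and length of stay are not in the documents. I assume that everyone in categories 3 to 7 is admitted, on a day uniform over study days 4 to 9 (six equally likely days), for L days counting the day of admission. In the strict reading the score is lost if day 10 falls within the stay. In the lenient reading the ±1 day window in 6.4.7 is used, and the score is lost only if days 9, 10 and 11 are all inpatient days.

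| L (days) | Strict: share lost | Placebo, ×4 | Window used: share lost | Placebo, ×4 |
|---|---|---|---|---|
| 3 | 2/6 = 0.33 | 1.3 | 1/6 = 0.17 | 0.7 |
| 5 | 4/6 = 0.67 | 2.7 | 3/6 = 0.50 | 2.0 |
| 7 | 6/6 = 1.00 | 4.0 | 5/6 = 0.83 | 3.3 |

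In the strict reading, stays longer than 7 days also lose all 4. For telmisartan, multiplying the same shares by about 1 gives 0.3 to 1.0 (strict) or 0.2 to 0.8 (window used).

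**Direction and upper bound.** As an illustration on the maximum-score comparison (not the mixed model itself), I deleted a fraction of categories 3 to 7 in both arms, using the exact odds-ratio-5 vector and scoring the categories 1 to 7:

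| Fraction deleted | Mean difference | One-sided power |
|---|---|---|
| 0 | 2.16 − 1.36 = 0.80 | 79.9% |
| 25% | 0.70 | 76.8% |
| 50% | 0.59 | 72.5% |
| 100% | 1.50 − 1.19 = 0.31 | 62.3% |

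With everything deleted, the odds ratio for category 1 against 2 among the remainder is (0.769/0.183)/(0.40/0.40) = 4.2 instead of 5.0. The last row overstates the practical loss, because only a participant who is in hospital at a visit loses that visit.

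**The case against.** The strongest reply is that 6.4.10 was not meant to reach Clinical Status. Section 6.3.1 describes study-specific procedures by naming swabs and research blood, and reading a chart is not something performed on a participant. Section 4.1.1 already requires in-hospital severity, and the release signed at entry makes the records available. This stands as a sensible account of intent, and it shows that the repair is easy. It does not close the gap: 4.1.1 calls for one maximum per participant, and no section assigns a record-derived score to day 4, 10 or 21.

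A reader might infer more than the documents support:

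- That the visit data omit exactly those who progress. They do not. Worsening at home (2.0 to 2.75), visits before admission and visits after discharge all stay in.
- That harm from telmisartan would be hidden. It would not. Hospitalisation and death count in the primary endpoint, and inpatient hospitalisation is an SAE under 7.1.2.
- That bias is certain or beyond repair by imputation. A likelihood-based mixed model keeps the earlier visits, and 9.3.1 does not prevent an imputation model from using the maximum score or hospitalisation status. But 9.3.1 does not specify this, and a missing-at-random assumption is doubtful when the current score determines whether it is seen.

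The size also rests on assumptions. Admission on days 4 to 9 sits just before day 10 and so favours a large loss there. The ICU timing in 2.1 ("the median time to ICU admission ranged from 10 to 12 days") concerns severe cases and is not in study days, so it does not settle the matter. Not sampling inpatients is a reasonable feasibility choice for a single-site outpatient pilot.

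**Conclusion.** The point holds as a gap between sections. Sections 4.1.1, 6.4.6, 6.4.10, 6.4.11 and 9.3.2 together leave an inpatient's visit-day Clinical Status without a source. Followed as written, the supplementary mixed model loses scores 3.0 to 6.0 through missingness caused by the outcome, and 9.3.1 does not deal with this.

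Under the planning vectors the loss is unequal by arm, at most about 4 against 1 participants. At day 10 that means roughly 1.3 to 4 placebo scores, or 0.7 to 3.3 for 3- to 7-day stays with the window used, conditional on the assumed admission days and stays. The risk is attenuation of the treatment-by-day effect if hospitalisation differs by arm. With similar hospitalisation in both arms the effect on the comparison could be small.

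The primary endpoint is not affected. The in-hospital samples are lost on either reading of 6.4.10, and that missingness is related to severity.

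**What to change.** - In 6.4.10, state that the bar covers in-person study visits, swabs and study blood draws, and does not cover abstraction of hospital records.
- In 9.3.2, state that for a participant in hospital at day 4, 10 or 21, Clinical Status for that day is taken from the hospital record under the signed release and enters the mixed model. State that death is scored 7.0 at later visits, or give another explicit handling of death.
- When the RAS, biomarker and viral comparisons are interpreted, count by arm the samples missed because of hospitalisation. The change above does not recover them.

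The cost is a few sentences in the protocol and the statistical section, plus a little chart abstraction for an expected handful of participants (about 5 of 40 under the planning vectors) whose records 4.1.1 already requires.
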